In a two year randomized, pilot study, two exercise training regimens (IMT and Aerobic) will be evaluated as compared to a control group by studying their effect on clinical end points and correlating them with central effects on cardiac remodeling specifically focusing on indices of left ventricular systolic and diastolic function (LVEDV, LVESV, EF, LV mass, LV longitudinal strain e' and E/e). Given that prior studies have predominantly studied aerobic exercise and there is no data available on the effect of IMT on cardiac remodeling or the peripheral effects, this study will provide us the unique opportunity to study IMT to determine its efficacy compared to aerobic training and will also provide mechanistic insight to overall change in symptoms. We anticipate that insights from this work will facilitate clinical implementation of exercise training and potentially provide insight into the use IMT as a therapy in individuals with HF who cannot perform aerobic exercise.

Overall Study Protocol: 75 HF patients will be enrolled. HF diagnosis will depend on physician diagnosis⁶⁵⁻⁶⁸. As part of this protocol 15 control subject will undergo a comprehensive pre- and post- assessments that will include a battery of physical function evaluations (aerobic, strength, and questionnaire indices), quality of life (QoL), and echocardiography. At the conclusion of their initial assessments they will continue with usual clinical care and will be retest on the same battery of assessment 12 weeks later. 60 patients already taking part in the VA MERIT F0834-R will have the option to additionally enroll into this study which would require them after enrollment into the Exercise Therapy protocol to complete an echocardiogram at baseline as well as post-intervention. All other parts of their participation will occur as part of the Exercise Therapy trial.

Table 4: Outline of protocol (by visit) for Controls group

Initial Assessment	Visit 1	Informed consent and physical exam, physical functional assessment battery (aerobic, strength, 6MWT, Hand Grip, and questionnaires), and echocardiographic
Exercise Training	12 weeks	Care as usual
Post assessment	Visit 38	Post-exercise assessment battery will mirror visit 1

Table 5: Outline of protocol (by visit) for Intervention Group

At time of randomization from VA MERIT F0834-R visit 3 of that protocol	Initial Assessment	Visit 1	Informed consent and echocardiographic

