Echocardiographic Assessment: All echocardiographic assessments will be performed at the West Roxbury VABHS campus where [name] is the Director of the Echo Lab. All subjects will have comprehensive echocardiographic studies in which all traditional echocardiographic parameters will be assessed, including comprehensive assessment of LV/RV structure and both systolic and diastolic function as recommended by the American Society of Echocardiography guidelines^{72,80}. Left ventricular end diastolic and end systolic volumes and ejection fraction (EF) will be measured by 2D (modified Simpson's method)⁷² as well as 3D TTE using an X5 probe and an offline analysis with Q-lab software (Phillips Burlington)⁸⁸ LV mass will be measured by the area length method⁷². For systolic assessments, in addition to traditional indices of LV volumes and EF, novel parameters, including longitudinal strain, strain rate, and LV twist will be measured^{55,87}. Diastolic function assessments will include traditional measures of mitral inflow velocity (E), mitral annular tissue velocity (E'), ratio of E/E', mitral flow propagation velocity as well as isovolumic relaxation time (IVRT) pulmonary venous flow profiles, and LV untwisting rate^{71,87}. Indices will also include measurement of left and right ventricular wall thickness, cavity dimensions, LA volume, right ventricular systolic function, cardiac output as well as pulmonary pressure. Please see appendix 2 for imaging protocol.

Functional Assessments and Exercise Training: Exercise assessments and exercise training for participants taking part in the intervention portion of the proposed study will be based off of and completed as part of the funded VA MERIT F0834-R to which this study is complements. For those that will be controls for the proposed study their assessment will be completed independent of the funded Merit. Functional assessments and training sessions will be completed at the JP VABHS.

The battery of physical function assessments will include aerobic, strength, inspiratory, and questionnaire indices to provide a comprehensive assessment of performance at baseline, after training.

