Project Time Line

Year I →→→→→	Year II →→→→→
Start Recruiting	Continue Recruiting
Start Assessments	Assessments
Start EX sessions	Exercise Sessions
	Manuscript Preparation

Year	Year 1		Year 2	
Time frame	0-6M	6-12M	12-18M	18-24M
Staffing	ES, RA, EX	ES, RA, EX	ES, RA, EX	ES, RA, EX
Enrollment	15	20	20	10
What will be happening	Setup/purchase supplies/recruitment/initial assessment /	Recruitment/assessments/interventions	Recruitment/Assessments/interventions	Recruitment/Assessments/interventions / manuscripts preparation

Study Team: Throughout the trial, [name] will meet regularly with co-investigators (4 times a year initially, and increasing to monthly when data analysis begins). Drs. [name], [name], [name], [name], [name], [name] all work in the VA or within close proximity and can presumably come to the VA campus for these meetings. However, phone teleconferencing will also be available for those who cannot participate in person. The skillsets and backgrounds of the investigators (as detailed in their biosketchs and the budget section) are extremely complementary and have contributed to a collegial and productive dynamic.

All study staff that will be working on this project are currently on staff at the VABHS. The echo sonographer, research assistant, and exercise physiologist will be an integral part of the team, they will coordinate recruitment, participant screening, enrollment, perform assessment visits, and follow ups. The current VABHS infrastructure through the Clinical Studies Unit (CSU) provide the ability for one exercise physiologist to perform the functional assessment while another performed the exercise trainings. This will allow this physiologist to remain blinded to the subject's intervention group thus eliminating tester bias.

Statistical Analysis: General considerations: This is a pilot study, described below are continuous outcome measures, primarily changes in function outcomes and gene expression and either continuous or categorical predictors. In all instances, outcome variables will be evaluated for violation of model assumptions and transformation of these variables will be considered as a remedy if needed. Analyses will generally be performed with an intent-to-treat approach, with sensitivity analyses performed to assess the role of drop-outs on the results.

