- Orthopedic exercise limitation
- Women who are pregnant, breastfeeding, or likely to become pregnant within the next 6 months
- Psychiatric hospitalization within the last 3 months
- Chronic ETOH or drug dependency.
- Exclusion criteria: Patients who have very poor acoustic windows in whom it is deemed that even with the use of contrast adequate image acquisition will not be possible will be excluded after initial assessment

B. Sources of research materials

All information pertaining to this project (e.g., screening forms, questionnaire data, interviews, cardiopulmonary testing results) will be held in the strictest confidence, will be kept in locked files, and will be available only to individuals directly involved with the project. Under no circumstances will individually identifiable data be released to anyone without written consent of the participant. Results will be published as group findings only. Assessment and treatment results will be discussed with the participant only and will only be used for research purposes unless patient give clearance for information to be provided for their own clinical care.

C. Potential Risk - During Assessments: - Controls only functional testing for all other patients will be completed as part of the Exercise Therapy protocol.

- During exercise testing assessments, just as when taking part in any exercise there are inherent risks associated. However, all candidates will undergo a cardiopulmonary exercise stress (CPX) test as part of their enrollment to provide baseline exercise indices, but also to provide a means to screen for safety prior to exercise training. Patients' physicians will refer only patients they expect to be stable. , A physician , will examine all study candidates before CPX and will also supervise the exercise tests to maximize safety. All testing will be completed by ACLS trained staff and during the stress test the physician will work in combination with an exercise physiologist to insure patient safety.

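### Separating the tester from the trainer can blind IMT versus aerobic, but not trained versus control, so the claim that tester bias is eliminated is too broad

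*Combined protocol and SAP*

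**What the plan says.** The Study Team paragraph, under Project Time Line, gives the mechanism: the Clinical Studies Unit will "provide the ability for one exercise physiologist to perform the functional assessment while another performed the exercise trainings". It then draws the conclusion that the testing physiologist stays blinded to the "intervention group thus eliminating tester bias". No other blinding measure for functional testing appears in the document.

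Four other places describe who is tested and where:

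- Overall Study Protocol, on controls: "As part of this protocol 15 control subject will undergo a comprehensive pre- and post- assessments". On the 60 Merit patients, for whom this protocol adds only echocardiograms: "All other parts of their participation will occur as part of the Exercise Therapy trial".
- Functional Assessments and Exercise Training: "For those that will be controls for the proposed study their assessment will be completed independent of the funded Merit".
- Human Subjects, C. Potential Risk - During Assessments: "Controls only functional testing for all other patients will be completed as part of the Exercise Therapy protocol".
- Study Team, on the sonographer, research assistant and exercise physiologist: "they will coordinate recruitment, participant screening, enrollment, perform assessment visits, and follow ups".

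Recruitment describes a separate route for controls (flyers, mailings, clinic). The paragraph before Exercise Training confines random assignment to aerobic versus IMT.

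**The concern.** The bias claim is stated without limit, but the mechanism behind it covers one comparison only. A tester who does not run the training sessions may be unaware whether a Merit patient does aerobic work or IMT. Nothing comparable keeps the tester unaware that a patient is a control.

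This matters because several tests in the battery depend on effort and on how hard the patient is urged on: treadmill peak VO2, the six-minute walk, maximum grip force and maximum inspiratory pressure. The opening of Materials and Method sets both regimens against control on clinical end points, and Aim 2 models peak VO2 across a sample that pools controls and trained patients. If the tester expects improvement in one group only and pushes differently at follow-up, part of any functional difference from control could come from testing rather than training. As the text stands, a reader would take those differences as assessor-blinded.

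**Working it through.** **Step 1. What the mechanism can mask.**

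| Comparison | How groups are formed | What hides group from the tester |
|---|---|---|
| IMT vs aerobic | Randomized within the Merit trial | Tester is not the trainer |
| Trained vs control | Controls recruited separately, not randomized | Nothing stated |

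Under this protocol, 15 of the 15 functionally tested patients are controls, and none of the 60 trained patients is functionally tested under it. The protocol under which a test is run therefore identifies the group. That the tester knows is an inference from this, but a strong one.

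**Step 2. When it would bias change.** Let s be the tester-induced shift for a group at a visit. The bias in the difference in change is

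(s trained, follow-up − s trained, baseline) − (s control, follow-up − s control, baseline).

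A shift that is equal at both visits gives zero. Only behaviour that differs between visits, and differently by group, matters.

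**Step 3. Which modelled outcomes are exposed.** The Statistical Analysis models peak VO2, VE/VCO2 slope and quality of life in Aim 2. Peak VO2 depends on effort. VE/VCO2 slope plausibly does so less. Quality of life is self-reported. The six-minute walk and grip appear in no specified model.

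**Step 4. The plan's Aim 2 figure.** Sample Size and Power states a detectable R² of 0.19 with 7 predictors, 75 subjects, alpha 5% and 80% power. With f² = 0.19/0.81 = 0.235, noncentrality 75 × 0.235 = 17.6, and 7 and 67 degrees of freedom, power is 0.845. Power of exactly 80% corresponds to R² = 0.175. The stated figure is slightly conservative and serves as a yardstick.

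**Step 5. Ceiling on the bias in Aim 2.** The documents give no size for tester bias. Assume a shift b of 0.25 to 0.5 SD of change. With p = 15/75 = 0.2 and q = 0.8, pq = 0.16. The share of outcome variance due to the shift is b²pq/(1 + b²pq):

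- b = 0.25: 0.0625 × 0.16 = 0.010, and 0.010/1.010 = 0.010
- b = 0.5: 0.25 × 0.16 = 0.040, and 0.040/1.040 = 0.038

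This is a ceiling, because it assumes that the echo predictors identify group perfectly. Against 0.19 it is 0.010/0.19 = 5% to 0.038/0.19 = 20%.

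**Step 6. A less extreme case.** Suppose one echo predictor differs between the groups by 0.91 SD and b = 0.5. Then r = 0.16 × 0.91 × 0.5 / √[(1 + 0.16 × 0.91²)(1 + 0.16 × 0.5²)] = 0.0728/1.085 = 0.067, so R² is about 0.005.

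**The case against.** The best defence is that the sentence may never have been meant to cover controls. Just before Exercise Training, the protocol uses the term intervention group for Merit patients assigned to aerobic or IMT. Blinding to that assignment is achievable, and this part of the defence stands. It does not rescue the unqualified clause about tester bias, which a reader will apply to every functional comparison.

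Parts of the mechanism are also unstated. The staff list names an exercise physiologist among those who recruit and enroll, but does not say that this is the tester. Nor do the documents say whether one person tests both controls and Merit patients. If different people do, tester and group are confounded, which is no better. Coded identifiers, physician supervision and a published method for the six-minute walk are in place, but none of them conceals control status.

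Three stronger readings are tempting and not supported:

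- *That the bias is a large part of what the design can detect.* Setting 0.25 to 0.5 SD against 0.91 SD gives 27% to 55%. But the 0.91 SD (reproduced: 30 versus 15, power 0.803) is stated for Aim 1, whose outcomes are echocardiographic. The plan specifies no trained-versus-control model for peak VO2, so the ratio describes no planned analysis.
- *That a tester-driven gap passes into Aim 2 as a training effect.* Those models regress function on echo measures and state no group term. The bias enters only as far as the echo predictors also separate the groups.
- *That peak VO2 should be adjusted for RER.* RER at follow-up is measured after training and may itself respond to it. Adjustment could remove real effect or add bias.

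**Conclusion.** The claim that tester bias is eliminated fails for trained versus control and may hold for IMT versus aerobic. The first part follows from the protocol's own account of who is tested, where, and how controls are found. That the tester actually knows control status is very probable but inferred.

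The consequence is moderate. It concerns effort-dependent tests, mainly peak VO2, and the comparison of regimens with control on clinical end points, for which the plan gives no model and the documents give no size of bias. In Aim 2 the ceiling is about 0.01 to 0.04 in R². That rests on the assumed 0.25 to 0.5 SD shift in change, a 60/15 split, and predictors that separate the groups perfectly. A reader might infer that the functional results are already shown to be biased; the documents show only that the stated protection is absent. Nothing here bears on the reading of the echocardiograms.

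**What to change.** 1. Restrict the blinding statement to IMT versus aerobic, and say plainly that functional comparisons with control are not assessor-blinded.
2. Assign recruitment, consent and booking of controls to the existing research assistant, not the testing physiologist.
3. Use one fixed script for encouragement and for how the end of a test is called, in all functional tests under this protocol, matched to the Merit trial's practice where possible. Clinical reasons for stopping a test are outside this point and stay with the investigators.
4. Report peak RER, already collected, by group and visit as a descriptive check on effort. Do not use it as a covariate.

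The cost is a small reassignment of tasks, a short script and one descriptive table, with no added patients, visits or measurements. Matching the Merit trial's practice depends on that study's agreement. Some unblinding will remain, because patients may reveal their group during testing.

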TIRE IMT will be administered progressively 40% week 1, 50% week 2, 60% the remainder of the protocol of the Maximal Inspiratory Pressure (MIP) and SMIP using a visual target that the patient watches on a monitor during the training. The visual target has been observed to facilitate inspiratory performance via biofeedback while the IMT progresses in respect to the work to rest ratio, with rest periods decreasing from 60 seconds at level A to 45, 30, 15, 10 and 10 seconds at levels B through F, respectively. TIRE IMT is characterized by through-range IMT with the need for patients to match or exceed 90% of the desired percentage of the on-screen target throughout the entire inspiratory effort (from RV to TLC). Thus, the training session continues until task failure indicated by an inability to match 90% of the on screen target, or until a maximum of 36 resisted breaths have been performed with an average duration of 25 minutes^{43,46}. Adherence and performance during TIRE training is captured automatically via TIRE computer software and each session is automatically performed at the desired workload (40% of MIP). An additional 20 minutes of IMT will be completed using the Threshold IMT. Threshold IMT will also be administered at progressively (40%, 50%, 60%) of MIP which will be adjusted each week to maintain a workload at 60% of MIP. Threshold IMT will require subjects to breathe through the mouthpiece of the Threshold device at a comfortable rate using diaphragmatic breathing techniques.

While prior studies have used a variety of training intervals and exercise intensities to achieve physiological benefits, in this protocol, we opted for a standardized 2-3x/week, 60 minute, 12 week regimen which is the best studied and validated training frequency and duration in which to achieve efficacy^{3, 40-43,48,78}.

Subject Retention: Utility of exercise will be emphasized to each exercise block throughout the course of the trial. If patients miss sessions, they will be immediately telephoned. A letter will be used to reach those who do not show for two or more sessions. As noted, exercise will be modified upon a patient's return from any missed sessions, but since exercise training is being administered on an intention to treat basis, the sessions will not be "made-up." Every effort will be made to foster a mutually supportive group dynamic, with the hope and intention to build expectations among the participants to support and encourage one another.

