Randomization will be generated using a SAS program based upon permuted random blocks of variable size to assure approximate balance over time and will be stratified by sex and statin use.

Aim 1a: *a) We hypothesize that exercise training will result in a decrease in Left ventricular end diastolic and end systolic volume and increase in ejection fraction (measures of morphology and systolic performance) as compared to the control group. b) We hypothesize that exercise training will increase mitral annular early diastolic velocity (e') as well as decrease the ratio (E/e') of early mitral inflow velocity (E) and e' (measures of diastolic performance). c) We hypothesize that both forms of training will be more beneficial compared to the control group and IMT will be non inferior to aerobic training regimen as related to cardiac remodeling.*

The outcomes for these hypotheses will be the outcome measures at baseline and at the end of follow-up. Parts a & b involve superiority tests using a mixed linear regression model comparing each active treatment group to the control group, specifically the interaction between time and treatment, with the ability to adjust for baseline values of the outcomes. Part c requires a test of non-inferiority between the two active treatments also involving a mixed model with a lower bound of 0.65 standard deviation units for each measure [see Sample Size and Power below].

Aim 2. *To explore the benefits of improved cardiac remodeling and physiology on functional and qualitative exercise training endpoints. a) We hypothesize that exercise training related cardiac improvements will lead to improved aerobic functional parameters (measured as peak VO_2 and VE/VCO_2 slope). b) We hypothesize that exercise training-related cardiac improvements will lead to improved quality of life.*

For hypotheses a & b, baseline and follow-up in peak VO_2 , VE/VCO_2 slope and quality of life will be the outcomes in separate mixed linear regression models using the measures of morphology, systolic and diastolic performance at evaluation times that were used as outcomes in aim 1 as predictors.

Exploratory Aim. Using the outcomes from aim 2 in separate mixed linear regression models using the predictors from aim 1 with the addition of potential confounders of peripheral function as determined by the supporting funded Merit to. We will evaluate the independent effect of central cardiac change on function.

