Sample Size and Power: With respect to superiority testing for mixed models in **aim 1**, power for an equivalent t-test will be used with sample sizes of 30 for the active treatment and 15 in the control group. This will result in the ability to detect a difference of 0.91 standard deviation [SD] units with 80% power, assuming an alpha level of 5%. For non-inferiority testing in aim 1, we propose a detectable difference of zero, with a lower boundary of 0.65 SD units, which provides 80% power using an alpha level of 5%⁷⁹.

In **aim 2**, a mixed linear regression model with 7 predictors would result in a detectable R^2 of 0.19 compared to a null model with 80% power, assuming alpha=5% and 75 subjects.

Study Data Management and Quality Control:

Prior to the initiation of the study, all investigators and research staff involved in clinical activities will meet to review study procedures and will complete all required trainings on data and patient privacy procedures. Documentation of any protocol breaches will be required. Each protocol violation will be evaluated by the PI and a determination made regarding the validity of any justification for the violation.

The study databases will be located at the VABHS. The clinical database with all research data will be stored on VA network drives and housed behind the VA firewall on VA owned and maintained servers, which are backed up on a regular schedule. All computers will have Kerberos passwords and come equipped with antivirus software. Data will not be stored on desktops or on non-VA servers. Study data will be coded with a unique study identifier for each participant and stored in a de-identified manner. A study data set without identifiable information will be used for all data analysis. Identifiable information will be collected for patient tracking and safety purposes, but will only be kept for as long as the study is active. De-identified clinical data will be stored separately from the participant's name, contact information, and real SSN. Access to the cross-walk file linking the participant's identifiers and their study data will be restricted to the project manager. This file will be destroyed according to CSP policy after the study ends. Study data will be retained and stored after the study ends according to federal and local VA regulations. Access to the study data is heavily restricted to

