Patients can also dilute the training effects if they modify their regimen by doing supplemental exercises at home (e.g., adding aerobic exercises by those in the IMT arm of the study). We will emphasize the priority of maintaining precise training regimens, and will offer patients the chance to cross-train as soon as the formal protocol is completed.

Although the current proposal employs well-validated exercise training parameters^{3,40-43, 68}, it is possible that the duration and intensity of the exercise training (either IMT or aerobic) may not be adequate to induce measurable changes in cardiac geometry and or to systolic and diastolic physiological performance.

Human Subjects

A. Risk to Subjects

A. Human Subjects Involvement and Characteristics

The study population will consist of 75 male and female participants age 50 and older who have been diagnosed with systolic heart failure (HF). Recruitment will include only Veterans and will focus on the VA Boston Healthcare System for recruitment. All patients must be cleared by their physician to participate in a supervised exercise environment.

As indicated in the Methods section:

Inclusion Criteria

- NYHA class II or III or AHA stage B or C HF with reduced ejection fraction (≤ 45), or AHA stage C with preserved ejection fraction despite a minimum of 6 weeks of optimal treatment
- Age ≥ 50 years

- Optimal therapy according to AHA/ACC and HFSA HF guidelines, including treatment with ACEI and beta-blocker therapy (for at least 6 weeks), or have documented reason for variation, including medication intolerance, contraindication, patient preference, or personal physician's judgment.
- ✓ Patients using statins will be enrolled; in the pilot study it was evident that most patients eligible for this study were on statins since prevalence of hypercholesterolemia is high and most clinicians are attentive to prescribing statins as part of their standard of care. While this is potentially a confounding issue, we will be certain that statin use is balanced in each arm.

Exclusion Criteria

- Major cardiovascular event or procedure within the prior 6 weeks.
- HF secondary to significant uncorrected primary valvular disease (except mitral regurgitation secondary to left ventricular dysfunction). If valve replacement has been performed, patient may not be enrolled for 12 months after this procedure.
- Dementia
- Severe COPD (FEV1<50%),
- PVD that would limit exercise- End-stage malignancy

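### The IMT versus aerobic non-inferiority test rests on intent-to-treat alone, so some foreseeable patterns of missed or supplemental training would make non-inferiority easier to declare, with no second analysis to show it

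*Combined protocol and SAP*

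**What the plan says.** Under Statistical Analysis, General considerations, the plan says: "Analyses will generally be performed with an intent-to-treat approach". The only supplement named there is "with sensitivity analyses performed to assess the role of drop-outs on the results". No per-protocol or adherence-based set is defined anywhere in the document.

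Under Aim 1 of the same section: "Part c requires a test of non-inferiority between the two active treatments also involving a mixed model with a lower bound of 0.65 standard deviation". This bound applies separately to every outcome. Sample Size and Power adds: "we propose a detectable difference of zero, with a lower boundary of 0.65 SD units". On the resulting power it says "which provides 80% power using an alpha level of 5" (per cent). It assumes 30 patients per active arm and 15 controls.

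Three other places bear on how training is delivered:

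- Subject Retention says that missed sessions are not replaced, "since exercise training is being administered on an intention to treat basis". This sentence is about giving the training, not about the analysis set. The same paragraph provides for a telephone call after a missed session and a letter after two or more.
- Limitations concedes: "Patients can also dilute the training effects if they modify their regimen by doing supplemental exercises at home". Its example is aerobic exercise added by patients in the IMT arm. The response is to stress the assigned regimen and to offer cross-training once the protocol is complete.
- Training Regimen #2 says that the TIRE software records adherence and performance automatically. No planned analysis uses these data.

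**The concern.** In a superiority comparison, imperfect delivery usually blurs the contrast and makes a positive claim harder. In a non-inferiority comparison, whatever brings the arms together helps the claim. A patient who misses many sessions but returns for the final echocardiogram is not a drop-out. Nor is an IMT patient who also trains aerobically at home. The planned sensitivity analyses would therefore miss both.

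At stake is how a positive Aim 1c result can be read. Under intent-to-treat alone, a finding that IMT is non-inferior could mean that IMT works nearly as well as aerobic training. It could also mean that the two programmes were not delivered distinctly enough to differ. The plan has no analysis that separates these readings. Materials and Method expects the work to help bring exercise training into clinical use, so the distinction matters even in a pilot.

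**Working it through.** **Inputs.** From Sample Size and Power: margin 0.65 SD, true difference zero, alpha 5%, 30 per active arm, 15 controls. Sidedness is not stated. No rate of adherence or home exercise is given, so every dilution figure below is an assumption.

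**Step 1: the plan's own figure.** The standard error of the difference, in SD units, is √(2/30) = 0.258. The noncentrality is 0.65/0.258 = 2.52. With 58 degrees of freedom and one-sided 5%, the noncentral t gives power 80.0% (normal approximation 80.9%). At one-sided 2.5% it would be 69.7%. The stated 80% therefore reproduces at one-sided 5%, which is used from here on.

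**Step 2: direction.** Let A and I be the full-adherence effects of aerobic training and IMT, so the IMT deficit is D = A − I.

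- Both arms lose a share f: the deficit becomes (1 − f)D. A real deficit shrinks.
- Aerobic sessions are missed: A falls and the deficit shrinks.
- IMT patients add effective aerobic work: I rises and the deficit shrinks.
- Sessions are missed mainly in the IMT arm: I falls and the deficit grows.
- Aerobic patients do extra aerobic work: A rises and the deficit grows.

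The first three favour declaring non-inferiority and the last two work against it.

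**Step 3: size where dilution favours the claim.** Take D = 0.65 SD, exactly the margin. After dilution f the deficit is 0.65(1 − f), which leaves 0.65f of room inside the margin. The noncentrality is 0.65f/0.258.

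| Dilution f (assumed) | Deficit in the intent-to-treat set (SD) | Chance of declaring non-inferiority |
|---|---|---|
| 0% | 0.650 | 5.0% |
| 10% | 0.585 | 8.1% |
| 20% | 0.520 | 12.6% |
| 30% | 0.455 | 18.4% |
| 50% | 0.325 | 34.4% |

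At the limit, if neither arm has any effect, the true difference is zero and non-inferiority is declared about 80% of the time, as in Step 1.

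**Step 4: size where it goes the other way.** Suppose both true effects are 0.5 SD and IMT alone loses 20% of its effect. A deficit of 0.5 × 0.20 = 0.10 SD appears and leaves 0.65 − 0.10 = 0.55 SD of room. Power falls from 80% to about 68%.

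**Step 5: does the control comparison cover this?** The superiority figure reproduces: 30 versus 15, 0.91 SD, two-sided 5%, gives 80.3%. For an effect of 0.65 SD, the same comparison has 52% power.

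**Step 6: power with a per-protocol set.** With 25 per arm and zero true difference, the noncentrality is 0.65/√(2/25) = 2.30 and power is 73%. By simulation, with the per-protocol patients a random subset of the 30, both sets pass together about 71% of the time with 25 per arm and 62% with 20. All figures are for one measure.

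**The case against.** **The direction is not fixed.** This stands. Without adherence by arm, nobody can say which way imperfect delivery will push the result. A reader might infer that poor delivery in general favours IMT. The documents do not support that, because Step 4 shows the opposite under an equally possible pattern. What remains is narrower: the one example the Limitations section gives is a pattern that favours the claim, and the plan could not detect either direction.

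**The 8 to 18% is an error rate only for one target.** This also stands. If the question is the effect of assignment to each programme as actually followed, a diluted deficit of 0.455 SD lies inside the margin and declaring non-inferiority is correct. The inflation matters only if the claim concerns the regimens when followed, and the documents do not say which is meant. The table also sits at the boundary case, whereas the plan assumes zero difference.

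**The controls are a safeguard.** In part. Hypothesis c pairs superiority of both arms over control with non-inferiority, so a failure of training in both arms should show there. But non-inferiority is not made conditional on that result, and power for a moderate effect is low. The controls are recruited separately and are not randomised with the exercise arms. The comparison also would not reveal aerobic exercise by IMT patients.

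**The plan says only that intent-to-treat applies generally, and it does act on adherence.** The wording leaves room for another set, but none is named, and one chosen after the data are seen would carry little weight. The calls, letters and emphasis on regimen may reduce the problem; they do not measure it. Limitations says home exercise can happen, not that it is expected.

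**A per-protocol set has its own bias.** It selects on behaviour after randomisation and can mislead either way. This is why it should accompany intent-to-treat and not replace it.

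**Conclusion.** The point holds as a gap in the analysis plan. The sample size and the stated power are not in error. Aim 1c has a single named analysis approach, its sensitivity analyses address only drop-outs, and the protocol itself names delivery problems that fall outside them.

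If dilution runs in the direction that favours the claim, and if IMT with full adherence is worse by the 0.65 SD margin, the chance of declaring non-inferiority rises from 5% to about 8 to 18% for dilution of 10 to 30%. This assumes 30 per arm and one-sided 5%, and the dilution range is not taken from the documents. If sessions are missed mainly in the IMT arm, the test becomes too hard to pass instead. A reader might conclude that intent-to-treat is the wrong primary analysis, or that a positive result would be invalid. Neither follows. For a pilot, this is a cheap improvement.

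**What to change.** In the Aim 1 paragraph of Statistical Analysis:

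1. Keep intent-to-treat for Aim 1c and add a per-protocol analysis, defined before the data are seen: both echocardiograms done, and attendance above a pre-set share of scheduled sessions. State the denominator, because two to three sessions a week for 12 weeks is anything from 24 to 36 sessions.
2. State that non-inferiority will be described as supported only if the two analyses are consistent, and that it will be interpreted alongside each arm's comparison with control.
3. Take attendance from the Merit study, where training is given. That records are kept is an inference from the calls and letters after missed sessions, so access should be confirmed. TIRE data alone are not enough: they cover about 25 of the 45 IMT minutes, and neither Threshold IMT nor aerobic training.
4. Exclude patients with supplemental training only if home exercise is recorded. No section describes recording it; one question at the post-assessment would do.

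**Cost.** One definition, one further analysis, an arrangement for attendance data and, if wanted, one added question. Power per measure is about 73% in a per-protocol set of 25 per arm and about 71% for both sets jointly (62% jointly with 20 per arm). Selection bias in the per-protocol set remains possible, which is why intent-to-treat is retained.
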